### 5.7.3 **Chain of custody of biological samples**

A full chain of custody is maintained for all samples throughout their lifecycle. The Principal Investigator at each center keeps full traceability of collected biological samples from the patients while in storage at the center until shipment or disposal (where appropriate) and keeps documentation of receipt of arrival.

The sample receiver keeps full traceability of the samples while in storage and during use until used or disposed of or until further shipment and keeps documentation of receipt of arrival.

AstraZeneca keeps oversight of the entire life cycle through internal procedures, monitoring of study sites and auditing of external laboratory providers.

Samples retained for future use are registered within the relevant sample tracking system at AstraZeneca.

### 5.7.4 **Withdrawal of Informed Consent for donated biological samples**

If a patient withdraws consent to the use of donated biological samples, the samples will be disposed of/destroyed, and the action documented. However, this does not result in withdrawal of the patient from the study and patient should continue until the end of study. If samples are already analyzed, AstraZeneca is not obliged to destroy the results of this research.

The Principal Investigator:

- Ensures patients' withdrawal of informed consent to the use of donated samples is communicated immediately to AstraZeneca
- Ensures that biological samples from that patient, if stored at the study site, are immediately identified, disposed of /destroyed and the action documented
- Ensures the laboratory (ies) holding the samples is/are informed about the withdrawn consent immediately and that samples are disposed of/destroyed, the action documented and the signed document returned to the study site
- Ensures that the patient and AstraZeneca are informed about the sample disposal

AstraZeneca ensures the central laboratory (ies) holding the samples is/are informed about the withdrawn consent immediately and that samples are disposed of/destroyed and the action documented and returned to the study site.

## **6. SAFETY REPORTING AND MEDICAL MANAGEMENT**

The Principal Investigator is responsible for ensuring that all staff involved in the study is familiar with the content of this section.

### **6.1 Definition of adverse events**

An adverse event is the development of an undesirable medical condition or the deterioration of a pre-existing medical condition following or during exposure to a pharmaceutical product, whether or not considered causally related to the product. An undesirable medical condition can be symptoms (e.g., nausea, chest pain), signs (e.g., tachycardia, enlarged liver) or the abnormal results of an investigation (e.g., laboratory findings, electrocardiogram). In clinical studies, an AE can include an undesirable medical condition occurring at any time, including run-in or washout periods, even if no study treatment has been administered.

The term AE is used to include both serious and non-serious AEs.

An AE (classified by preferred term) that occurs during the double-blind treatment period will be considered a TEAE (Treatment Emergent Adverse Event) if it was not present prior to the first dose of study drug, or it was present prior to the first dose of study drug but increased in severity during the double-blind treatment period. An AE that occurs more than 28 days after the last dose of study medication will not be counted as a TEAE.

## 6.2 Definitions of serious adverse event

A serious adverse event is an AE occurring during any study phase (i.e., screening, treatment and follow-up), that fulfils one or more of the following criteria:

- Results in death
- Is immediately life-threatening
- Requires in-patient hospitalization or prolongation of existing hospitalization
- Results in persistent or significant disability/incapacity or substantial disruption of the ability to conduct normal life functions
- Is a congenital abnormality or birth defect
- Is an important medical event that may jeopardize the patient or may require medical intervention to prevent one of the outcomes listed above

For further guidance on the definition of a SAE, see [Appendix B](#) to the Clinical Study Protocol.

## 6.3 Recording of adverse events

### 6.3.1 Time period for collection of adverse events

Serious Adverse Events (SAEs) will be collected from the time of signature of informed consent throughout the treatment period and including the follow-up period.

Adverse Events (AEs) will be collected from randomization throughout the treatment period and including the follow-up period. See Section 3.9.3.2 for details regarding AE collection for subjects who are followed by modified follow-up after premature discontinuation of IP.

### 6.3.2 Follow-up of unresolved adverse events

Any AEs that are unresolved at the follow up visit in the study are followed up by the Investigator for as long as medically indicated, but without further recording in the eCRF. AstraZeneca retains the right to request additional information for any patient with ongoing AE(s)/SAE(s) at the end of the study, if judged necessary.

### 6.3.3 Variables

The following variables will be collected for each AE:

- AE (verbatim)
- The date when the AE started and stopped
- Intensity or changes in intensity

- The investigator should use the [National Cancer Institute \(NCI\) Common Terminology Criteria for Adverse Events \(CTCAE\) version 4.0](#). For terms not specified as part of NCI- CTCAE, the following guidelines should be used to determine grade:
  - **Grade 1, Mild:** Asymptomatic or mild symptoms that the patient finds easily tolerated. The event is of little concern to the patient and/or of little-or-no clinical significance; clinical or diagnostic observations only; intervention not indicated
  - **Grade 2, Moderate:** The patient has enough discomfort to cause interference with or change in some of their age-appropriate instrumental activities of daily living (e.g. preparing meals, shopping for groceries or clothes, using the telephone, managing money); local or non-invasive intervention indicated
  - **Grade 3, Severe:** The patient is incapacitated and unable to work or participate in many or all usual activities. The event is of definite concern to the patient and/or poses substantial risk to the patient's health or well-being; Likely to require medical intervention and/or close follow-up, including but not limited to hospitalization or prolongation of hospitalization
  - **Grade 4, Life-threatening:** The patient was at immediate risk of death from the event as it occurred
  - **Grade 5, Death:** Related to AE

Grade 4 & 5 are SAE criteria and collected as SAE in the AE eCRF module. The following variables will be collected:

- Whether the AE is serious or not
- Investigator causality rating against the Investigational Product (yes or no)
- Action taken with regard to investigational product
- AE caused patient's withdrawal from study (yes or no)
- Outcome

In addition, the following variables will be collected for SAEs:

- Date AE met criteria for serious AE
- Date Investigator became aware of serious AE
- AE is serious due to
- Date of hospitalization
- Date of discharge

- Probable cause of death, if applicable
- Date of death, if applicable
- Autopsy performed, if applicable
- Causality assessment in relation to Study procedure(s)
- Description of AE

It is important to distinguish between serious and severe AEs. Severity is a measure of intensity whereas seriousness is defined by the criteria in Section 6.2. An AE of severe intensity need not necessarily be considered serious. For example, nausea that persists for several hours may be considered severe nausea, but not a SAE unless it meets the criteria shown in Section 6.2. On the other hand, a stroke that results in only a limited degree of disability may be considered a mild stroke but would be a SAE when it satisfies the criteria shown in Section 6.2.

#### 6.3.4 Causality collection

The Investigator will assess causal relationship between Investigational Product and each Adverse Event and answer ‘yes’ or ‘no’ to the question ‘Do you consider that there is a reasonable possibility that the event may have been caused by the investigational product?’

For SAEs causal relationship will also be assessed for other medication and study procedures and additional study drug. Note that for SAEs that could be associated with any study procedure the causal relationship is implied as ‘yes’.

A guide to the interpretation of the causality question is found in [Appendix B](#) to the Clinical Study Protocol.

#### 6.3.5 Adverse events based on signs and symptoms

All AEs spontaneously reported by the patient or reported in response to the open question from the study personnel: ‘*Have you had any health problems since the previous visit/you were last asked?*’ or revealed by observation will be collected and recorded in the eCRF. When collecting AEs, the recording of diagnoses is preferred (when possible) to recording a list of signs and symptoms. However, if a diagnosis is known and there are other signs or symptoms that are not generally part of the diagnosis, the diagnosis and each sign or symptom will be recorded separately.

#### 6.3.6 Adverse events based on examinations and tests

The results from protocol mandated laboratory tests and vital signs will be summarized in the clinical study report. Deterioration as compared to baseline in protocol-mandated laboratory values and vital signs should therefore only be reported as AEs if they fulfil any of the SAE criteria or are the reason for discontinuation of treatment with the investigational product.

If deterioration in a laboratory value/vital sign is associated with clinical signs and symptoms, the sign or symptom will be reported as an AE and the associated laboratory result/vital sign will be considered as additional information. Wherever possible the reporting Investigator uses the clinical, rather than the laboratory term (e.g. anemia versus low hemoglobin value). In the absence of clinical signs or symptoms, clinically relevant deteriorations in non-mandated parameters should be reported as AE(s).

Deterioration of a laboratory value, which is unequivocally due to disease progression, should not be reported as an AE/SAE.

Any new or aggravated clinically relevant abnormal medical finding at a physical examination as compared with the baseline assessment will be reported as an AE.

#### 6.3.7 Liver enzymes

If a patient meets any of the following criteria, please refer to [Appendix D](#) for further instruction:  $AST \geq 3xULN$ ,  $ALT \geq 3xULN$ , total bilirubin  $\geq 2xULN$ .

#### 6.3.8 Disease progression

Changes in patient condition that are due to progression of the disease for which the investigational product is being studied (for example, anemia or CKD) should not be considered AEs or SAEs. This includes an increase in the severity of the disease under study, and an increase in the symptoms of the disease under study. Roxadustat is being studied for the treatment of anemia in CKD. CKD progression should therefore not be considered an AE or SAE. Acute kidney injury, when meeting diagnostic criteria (i.e. based on serum creatinine values or urine output), can be considered an AE or SAE. AEs or SAEs that cause anemia should be recorded, but anemia for which no cause is found other than CKD should not be reported as an AE or SAE.

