## LIST OF ABBREVIATIONS AND DEFINITION OF TERMS

The following abbreviations and special terms are used in this study Clinical Study Protocol.

Abbreviation or special term	Explanation
AE	Adverse event
ALP	Alkaline phosphatase
ALT	Alanine aminotransferase
ANCOVA	Analysis of covariance model
Anti-HCV antibody	Anti-hepatitis C virus antibody
AST	Aspartate aminotransferase
BP	Blood pressure
CABG	Coronary artery bypass graft surgery
CBC	Complete Blood Count
CKD	Chronic kidney disease
CKD-NDD	Chronic kidney disease-non-dialysis dependent
CSA	Clinical Study Agreement
CSE	Composite safety endpoint
CSR	Clinical Study Report
CMH	Cochran-Mantel-Haenszel
CTCAE	Common Terminology Criteria for Adverse Event
CV	Cardiovascular
DSMB	Data and Safety Monitoring Board
DVT	Deep vein thrombosis
EC	Ethics committee, synonymous to Institutional Review Board(IRB)
ECG	Electrocardiogram
eCRF	Electronic case report form
eGFR	Estimated glomerular filtration rate
EOS	End of Study
EOT	End of Treatment
EQ-5D-5L	EuroQol Health Utility Index
FACT-An	Functional Assessment of Cancer Therapy-Anemia
ESRD	End-stage Renal Disease
FAS	Full Analysis Set
GGT	Gamma-glutamyl transferase
GCP	Good Clinical Practice
GMP	Good Manufacturing Practice

Abbreviation or special term	Explanation
Hb	Hemoglobin
HBsAg	Hepatitis B surface antigen
hCG	Human chorionic gonadotropin
HIF	Hypoxia-inducible factor
HIF-PHI	HIF prolyl hydroxylase inhibitor
HIV	Human immunodeficiency virus
HR	Heart rate
HRQoL	Health Related Quality of Life
hsCRP	High-sensitivity C-reactive protein
IB	Investigator's brochure
ICF	Informed consent form
ICI	International Co-ordinating Investigator, If a study is conducted in several countries the International Co-ordinating Investigator is the Investigator co-ordinating the investigators and/or activities internationally.
IERC	Independent Endpoint Review Committee
IP	Investigational Product
IRB	Institutional Review Board
ITT	Intention To Treat
IV	Intravenous
IVRS	Interactive Voice Response System
IWRS	Interactive Web Response System
KDIGO	Kidney Disease Improving Global Outcomes
KDOQI	Kidney Disease Outcomes Quality Initiative
LDL	Low-density lipoprotein
LFT	Liver function test
LLN	Lower limit of normal
MACE	Major adverse cardiovascular events; defined as a composite endpoint of death from any cause, non-fatal myocardial infarction or non-fatal stroke

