### 2.2 Secondary objectives

Secondary Efficacy Objectives:	Outcome Measure:
The efficacy of roxadustat compared to placebo based on Hb response and level during the study	Proportion of total time of Hb $\geq$ 10 g/dL from week 28 to week 52. Proportion of total time of Hb within the interval of 10-12 g/dL from week 28 to week 52
The efficacy of roxadustat compared to placebo based on Hb response in inflamed subjects	Mean change in Hb from baseline to the subjects mean level between week 28 to week 52 in subjects with baseline high-sensitivity C-reactive protein (hsCRP) greater than the Upper Limit Normal (ULN)
The effect of roxadustat compared to placebo on Low-density lipoprotein (LDL) cholesterol	Mean change in LDL cholesterol from baseline to week 24
The need for rescue therapy in subjects treated with roxadustat as compared to placebo	Time-to-first (and proportion of subjects receiving) instance of receiving intravenous (IV) iron, red blood cell (RBC) transfusions, or erythropoietin analogue as rescue therapy. Time-to-first (and proportion of subjects receiving) instance of receiving red blood cell (RBC) transfusions as rescue therapy.
The effect of roxadustat on anemia symptoms and health-related quality of life (HRQoL) based on comparison with placebo	Changes in generic HRQoL as measured by the SF-36 (Version 2, standard)
The effect on the CKD progression of roxadustat as compared to placebo	Annual rate of eGFR change in log scale, calculated as the linear slope of log (eGFR values) to prior to initiation of dialysis/kidney transplant

Secondary Safety Objectives:	Outcome Measure:
To evaluate the safety and tolerability of roxadustat.	Adverse events (AEs), serious adverse events (SAEs). Changes in vital signs, electrocardiogram (ECG) and laboratory values.

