### 5.2.1 Cardiovascular events

MACE+ events (death, non-fatal MI, non-fatal stroke, heart failure requiring hospitalization and unstable angina leading to hospitalization) should be reported as SAEs in the eCRF. Deep vein thrombosis, pulmonary embolism, vascular access thrombosis and hypertensive emergencies will also be reported and adjudicated.

SAEs will be screened against a pre-specified list of MedDRA preferred terms to identify potential MACE+ events plus the rest of the CV events listed above. When a potential CV event is identified, the principal investigator will be contacted to collect supporting medical records; once the clinical endpoint packet is compiled, blinded adjudication of candidate CV events will be conducted by the Independent Endpoint Review Committee (IERC) as described in the IERC charter.

Independent Event Review Committee Charter (IERC) contains complete information regarding the cardiovascular events and criteria for adjudication.

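### Section 6.3.8 exempts CKD and anemia progression from SAE reporting with no exception for fatal or hospitalized cases, which conflicts with Section 5.2.1, where deaths and heart-failure admissions reach adjudication as SAEs

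*Protocol*

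**What the plan says.** **The exemption.** Under Section 6.3.8, changes due to progression of the disease for which the product "is being studied (for example, anemia or CKD) should not be considered AEs or SAEs". The section extends this to greater severity and more symptoms, and then states that "CKD progression should therefore not be considered an AE or SAE". The one kidney event that it keeps reportable is worded permissively: "Acute kidney injury, when meeting diagnostic criteria (i.e. based on serum creatinine values or urine output), can be considered an AE or SAE".

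**The endpoint rule.** Section 5.2.1 lists the MACE+ components, including death without restriction by cause and heart failure leading to admission, and says that they should be reported as SAEs in the eCRF. It then describes how events reach the Independent Endpoint Review Committee (IERC): "SAEs will be screened against a pre-specified list of MedDRA preferred terms to identify potential MACE+ events" and the other adjudicated CV events. A hit leads to a request for records and then to blinded adjudication. The abbreviation list gives MACE as "defined as a composite endpoint of death from any cause, non-fatal myocardial infarction or non-fatal stroke".

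**The objective.** Section 2.1 makes contributing adjudicated CV data to the pooled analyses the primary safety objective. Section 2.2 has as a secondary efficacy objective "The effect on the CKD progression of roxadustat as compared to placebo", which is tested ninth in the sequence of Section 8.6.5.

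**The concern.** The two sections give a site opposite instructions for the same event. Take a stage 5 patient who dies of uremia, or one admitted with fluid overload that the site regards as worsening CKD. Under 6.3.8 the event is neither an AE nor an SAE. Under 5.2.1 the death is an SAE, and so is the admission if it is heart failure. Whether the admission is heart failure or CKD progression is then decided at the site, before any adjudicator sees it.

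If a site follows 6.3.8, the event does not enter the preferred-term screen. Whether roxadustat alters CKD progression is itself an open question in this trial, so the number of events given that label could differ between arms without any unblinding. That would bias the CV comparison rather than merely thin it.

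**Working it through.** No figure in the protocol is in dispute, so the main check is of the text.

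**1. Does the SAE definition rescue the serious cases?** No. Section 6.2 defines an SAE as an AE that also meets a seriousness criterion, such as "Requires in-patient hospitalization or prolongation of existing hospitalization". If 6.3.8 says that the event is not an AE, the criteria for death and hospitalization are never reached.

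**2. Does another section show a narrower exemption?** Yes. Section 6.3.6 says: "Deterioration of a laboratory value, which is unequivocally due to disease progression, should not be reported as an AE/SAE". That is limited to unequivocal cases, and the same section has deteriorations in mandated laboratory values and vital signs reported when they meet SAE criteria. Section 6.3.8 has neither limit.

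**3. Which events are exposed?**

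| Event, attributed by the site to CKD progression | Section 6.3.8 | Section 5.2.1 | Composite |
|---|---|---|---|
| Death | Not an AE or SAE | SAE, screened | MACE and MACE+ |
| Fluid-overload admission that could be heart failure | Not an AE or SAE | SAE if heart failure | MACE+ only |
| Acute kidney injury meeting criteria | May be an AE or SAE | Not listed | None |

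**4. Do other data streams reach the screen?** Section 5.3.2 collects all hospitalizations at each visit. Sections 3.9.3 and 3.10 collect vital status. Section 3.9.3.2 asks for potential endpoints in the 28 days after permanent discontinuation. After that, for patients in modified follow-up, it asks for SAEs plus information relevant to adjudicated events. Section 5.2.1 screens SAEs, and no section says that the hospitalization or vital-status data are screened too.

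**5. What would a loss do? Illustration only.** The protocol gives no loss rate, so the shares below are assumptions. D = 465 is the program MACE target over three studies (Section 8.2). The illustration applies this protocol's rule to all three, although the AE rules of the other two studies are not shown.

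Equal loss: with 1:1 allocation the standard error of the log hazard ratio is about 2/√D, so the 95% limits lie a factor exp(1.96 × 2/√D) either side of the estimate.

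- No loss, D = 465: exp(1.96 × 2/21.56) = 1.199
- 5% loss, D ≈ 442: 1.205
- 10% loss, D ≈ 419: 1.211
- 20% loss, D = 372: 1.225

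Unequal loss: with a true ratio of 1.0, the observed ratio is (1 − loss on roxadustat)/(1 − loss on placebo).

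- 10% against 5%: 0.90/0.95 = 0.947; reversed, 0.95/0.90 = 1.056
- 15% against 5%: 0.85/0.95 = 0.895; reversed, 0.95/0.85 = 1.118

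Equal loss barely widens the interval. Unequal loss moves the estimate, in a direction that depends on which arm loses more.

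**The case against.** The best defense is that 5.2.1 is the specific rule for endpoint events and 6.3.8 the general one, so a careful site would report the death or heart-failure admission as an SAE. Deaths also have a second route. Vital status is followed to study closure after drug discontinuation, asked for at the end-of-study contact, and sought from public sources even after consent is withdrawn, where local rules allow. Since MACE counts death from any cause, a death known in this way could count whatever cause the site assigned. Hospitalizations are recorded with reasons and dates regardless of AE status. The IERC charter and the pooled analysis plan, which are not shown, may close the gap.

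Much of this stands, and it rules out stronger readings.

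- A reader might infer that 6.3.8 removes fatal and hospitalized cases outright. It does not: 5.2.1 still requires them as SAEs, and the finding is an unresolved conflict.
- A reader might infer that SAEs are the only source for adjudication. Section 3.9.3.2 adds other information for patients who have stopped study drug.
- A reader might infer that renal harm is hidden. Creatinine, eGFR slope and dialysis start are all captured, and the data safety board can merge treatment codes with accumulating data. How dialysis start is tabulated may be left to the SAP.
- A reader might multiply 465 by an assumed share of deaths blamed on CKD. No such share is in the protocol, and the product would count every exposed death as lost despite the vital-status follow-up.

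The defense does not supply a sentence giving 5.2.1 precedence, or one linking the hospitalization and vital-status data to the screen. The fluid-overload admission is the weaker spot, because nothing comparable to vital status would flag it as a possible endpoint.

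**Conclusion.** The conflict between 6.3.8 and 5.2.1 is real and bears on the primary safety objective. Followed literally, 6.3.8 lets a site keep a death or fluid-overload admission labelled as CKD progression out of the described route to the IERC. For deaths, vital-status follow-up reduces the risk of losing the event. For possible heart-failure admissions, which count in MACE+ but not MACE, the record exists but has no stated path to screening.

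No size of effect can be derived from the documents. The ratios above show direction and sensitivity under assumed losses; they do not predict bias in this trial. The conclusion assumes that the unseen charter and pooled plan do not already draw on the other data streams. Leaving non-serious progression that is not an endpoint event out of AE reporting is a deliberate choice and is not criticized here.

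**What to change.** Add to Section 6.3.8: *This exemption does not apply to events listed in Section 5.2.1. Every death and every potential adjudicated event, including an unplanned admission for fluid overload or dyspnea that could be heart failure, is reported as an SAE and screened, whatever its attributed cause. The rule on planned admissions in Appendix B is unchanged.*

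The last sentence matters. A wider rule making every admission an SAE would contradict Appendix B, under which planned admissions for existing illness are not AEs unless the illness worsens unexpectedly.

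Version 6.0 is dated 31 August 2018 and Section 9.3 estimates study end by Q3 2018, so new wording alone will change few reports. Before database lock, reconcile the hospitalization and vital-status records already collected against the SAE and adjudication records, blind to treatment, and send unmatched potential events through the Section 5.2.1 screen.

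The cost is a short protocol addition with site guidance, some additional SAE reports for CKD-related admissions, and the reconciliation work. No new data collection is planned, though supporting records would be requested for unmatched events.
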